13.3.5 Outcome

The clinical course of all AEs should be followed until a medical outcome is determined (resolution, stabilization, or determination that it was unrelated to study participation). If a

subject becomes pregnant within 90 days of receiving rt-PA, follow-up should be obtained to establish the pregnancy's outcome. The clinical outcome of all AEs will be recorded as follows:

Death	
Recovered	Patient returned to baseline status.
Not Yet Recovered	Patient did not recover and symptoms/sequelae continue.
Recovered with Sequelae	Patient recovered but with clinical sequelae from the event.

13.3.6 Treatment or Action Taken

AEs and SAEs will be categorized by the actions taken in response to the event:

Intervention	Surgery or other invasive procedure
Non-surgical Treatment	Drug initiation, interruption, dose reduction, or
	discontinuation
None	No action was taken.

13.4 Reporting Requirements for Serious Adverse Events

All observed or volunteered SAEs occurring from randomization through 24 months following randomization, regardless of treatment group or suspected causal relationship to the research study, must be recorded on the designated Serious Adverse Event CRF and submitted to the DCC. The Clinical Center investigator should also report any SAE occurring after a subject has completed or discontinued study participation if it was possibly related to prior rt-PA exposure.

If the investigator should become aware of the development of cancer or congenital anomaly in a subsequently conceived offspring of a female subject, this should be reported as a SAE. The Clinical Center investigators must use the following procedure for reporting SAEs:

 Report any SAE that occurs within 24 months after randomization to the ATTRACT Trial Clinical Coordinating Center (CCC) at the Washington University School of Medicine. A description of the event should be reported on the electronic Serious Adverse Event CRF and e-mailed or faxed within 24 hours of knowledge of the event (Monday-Friday) to:

> [name]. Principal Investigator, ATTRACT Trial Mallinckrodt Institute of Radiology [name] [contact] [contact]

E-Mail: [contact]

- 2. Report the SAE to the Clinical Center's local IRB per its regulations. If the event causes death or is life-threatening, this must be done **within 24 hours of knowledge of the event**.
- 3. Electronically transmit the Serious Adverse Event CRF to the Data Coordinating Center.
- 4. In reporting SAEs, the investigator should provide any potentially relevant information on subject demographics; pre-existing conditions; the event's description; its date/time of onset, severity, and treatment; results of diagnostic testing; the duration of sequelae; and outcome if known. Information on suspect medications including dose, route of administration, frequency, dates, lot number, expiration date, and concomitant medications should be given.
- 5. Deaths: Any report of a patient death should be accompanied by a Death CRF, a Follow-Up CRF, an End of Study CRF, an Adverse Event CRF, a Serious Adverse Event CRF, a statement of the pertinent details, and the death records/certificate and autopsy report (if performed). When reporting a death, the primary event or condition that caused or contributed to the fatal outcome should be reported as the SAE (death is the outcome of that SAE). If the cause of death is unknown at the time of reporting, report "Unexplained Death".

At the CCC, [name] (the ATTRACT Trial Principal Investigator and IND Holder) will review the SAE report and obtain any needed additional clarifications concerning the event by direct telephone conversations and/or e-mail with the Clinical Center investigator(s). The Clinical Center investigator's description and categorization of the SAE per the criteria in Section 13.3, and any additional relevant information, will then be reviewed at the CCC by the ATTRACT Trial Safety Officer. The Safety Officer will determine if the SAE was properly categorized. If not, he will provide [name] and the Clinical Center investigator with a modified categorization, along with a brief written rationale for re-categorizing the SAE. In nearly all instances, the Safety Officer's categorization will be considered the CCC's final categorization of the SAE. However, if a Clinical Center investigator continues to believe that a SAE was unexpected or possibly, probably, or definitely related to use of rt-PA, then the event will be reported as such.

13.4.1 Expedited Reporting of SAE that are Unanticipated Problems

The CCC will evaluate each SAE to determine if it fulfills the criteria for being a UP (see Section 13.1.3). [name] (Principal Investigator and IND Holder) will notify the NHLBI Project Officer; the DSMB Executive Secretary; the Washington University Human Research Protection Office; the FDA (fax [name]); Genentech Drug Safety ([contact], [contact] or [contact]); the ATTRACT Steering Committee, and the Clinical Center

investigators of any SAE that is a UP within 7 calendar days of first learning of the event. The Clinical Center investigators are then responsible for notifying their respective IRBs of the UP.

13.4.2 IND Safety Reports

[name] is the Primary Medical Monitor and is responsible for timely submission of the Medwatch 3500a form to the FDA. **Within 15 calendar days** after initial knowledge of any SAE categorized as unexpected and possibly, probably or definitely related to the use of rt-PA, [name] will send a written IND Safety Report to (a) the FDA (faxed to [name]); (b) Genentech Drug Safety [contact] or [contact]); (c) the NHLBI Project Officer; (d) the Washington University Human Research Protection Office; (e) the DSMB Executive Secretary; (f) the ATTRACT Steering Committee; and (g) the Clinical Center investigators. This Report will include an Analysis of Similar Events, per 21 CFR 312.32. The Clinical Center investigators are then responsible for providing this Report to their IRBs.

We expect that this strategy will allow the identification of serious or systematic hazards in a timely fashion, facilitating corrective action and appropriate reporting to regulatory agencies.

Contact numbers for [name] (ATTRACT Trial Principal Investigator, IND Holder, and Primary Medical Monitor) and [name] (ATTRACT Trial Safety Officer) are below:

Primary Medical Monitor

[name]. Principal Investigator, ATTRACT Trial Mallinckrodt Institute of Radiology [name] [contact] [contact] E-Mail: [contact]

ATTRACT Trial Safety Officer

[name]., Ph.D. Safety Officer, ATTRACT Trial Mallinckrodt Institute of Radiology [name] [contact] [contact] E-Mail: [contact]

For questions regarding AE or SAE reporting, the Clinical Center investigators may contact [name] or the Genentech Medical Science Liaison ([name]., [contact], [contact]) at any time. Information on all SAEs, any pregnancy that occurs within 3 months of rt-PA use in female subjects (including follow-up on the pregnancy's outcome), all annual reports to the FDA, the final Clinical Study report, and any literature articles that result from the ATTRACT Trial will be copied to the Genentech Medical Science Liaison.

13.5 Reporting Requirements for Non-Serious AEs

All non-serious AEs that occur from randomization through 30 days after randomization, or that occur within 30 days after a PCDT procedure that is performed at any time during the follow-up period, must be reported to the DCC on the Adverse Events CRF. Note: if recurrent VTE or bleeding occurs beyond 30 days but the event does not meet the Section 13.1.1 criteria for a SAE, the event should not be reported to the DCC as an AE. However, the event must still be reported to the DCC as a possible outcome event - a Suspected VTE or Suspected Bleeding CRF would need to be submitted to the DCC along with any relevant source documentation.

13.6 Reporting Requirements for Unanticipated Problems that are not SAEs

Any UP (whether or not it causes an AE) should be reported to [name] by e-mail or fax within 24 hours of knowledge of the event or problem (Monday-Friday), and should also be reported to the site's local IRB per its regulations. For further information on UP reporting, please see the policy at http://www.hhs.gov/ohrp/policy/AdvEvntGuid.htm or **Appendix 15**.

The CCC will report any UP along with a description of any corrective action planned or taken in response to the UP to the NHLBI Project Officer, the DSMB Executive Secretary, the FDA, the Washington University Human Research Protection Office, the ATTRACT Steering Committee, Genentech Drug Safety, and the Clinical Center investigators within 30 calendar days (or within 7 calendar days if the UP is fatal, life-threatening, or serious). The Clinical Center investigators are then responsible to notify their local IRBs of any UP of which they are notified by the CCC.

14 DATA REPORTING, PROCESSING AND QUALITY CONTROL

14.1 Training of Field Personnel and Standardization of Assessments

14.1.1 Clinical Outcomes

Before starting the study, all study nurses will complete standardized training on the proper acquisition and reporting of data. This will be accomplished with: a) the Manual of Procedures; b) a start-up Investigator's Meeting with hands-on training and practice sessions using the measurement scales; c) use of a full color, plasticized graphic visual aid for grading signs of PTS using Villalta PTS Scale; d) use of published tables/descriptions that instruct examiners on use of Basic CEAP and the VCSS system, and; e) an on-line training module for the electronic remote data capture system. Administration of the PTS instruments is detailed in Section 8.9.

14.1.2 Imaging Outcomes (Ultrasonography and Venography)

The following steps will be taken to ensure optimal acquisition and quality, standardization, and interpretation of imaging studies: 1) close communication between the Data Coordinating

Center, Clinical Centers, Ultrasound Core Laboratory, and Clinical Coordinating Center in the development of training, operations, and adjudication manuals, aids (including DVDs), and case report forms; 2) diligent credentialing of Ultrasound Substudy Center sonographers (they will have recognized certifications for trained vascular technologists and significant experience with performance of venous Duplex ultrasound exams), vascular ultrasound laboratories (accreditation by American College of Radiology or Intersocietal Commission for Accreditation of Vascular Laboratories), the endovascular physicians (subspecialty board certification), and the Clinical Centers (accredited by the Joint Commission on the Accreditation of Healthcare Organizations); 3) use of high quality venous Duplex ultrasound and digital venography; 4) training sessions for ultrasonography personnel at the yearly Investigator Meetings; 5) certification of individual sonographers by the Ultrasound Core Laboratory based on review of at least 2 random venous Duplex ultrasound examinations performed using the ATTRACT Duplex protocol (Appendix 12); 6) independent central interpretation of ultrasound (Ultrasound Core Laboratory) and venogram (DCC) examinations by 2 blinded expert readers, with involvement of a third reader to resolve discrepancies; and 7) ongoing quality control feedback to the Clinical Centers from the central reading facilities at the DCC and Ultrasound Core Laboratory.

14.2 Data Acquisition, Monitoring and Quality Control

Subject data will be collected via a remote-entry web-based Electronic Data Capture (EDC) application. This system utilizes Microsoft's ASP.NET AJAX technology as a method of clientserver communication and uses Microsoft SQL 2008 R2 server as the database engine. All data exchange is encrypted using the Secure Sockets Layer (SSL) communication protocol. Application level security is a role-based security model. This system incorporates on-line controls and validation, and web-based query generation and response options. Where appropriate, the database will only accept data within pre-defined ranges, verify that entered dates are consistent for individual subjects, force entry of compulsory fields that must be completed before subsequent data entry, and cross-reference data to check for internal consistency. Entered data that is inconsistent, missing, or erroneous will be flagged for review by DCC staff; if these concerns cannot be resolved with certainty within the Web-based system, DCC staff will contact the Clinical Center for clarification. As a backup, PDF versions of the Case Report Forms will be available on the study website, and completed forms can be faxed to the DCC. At regular intervals, the data will be scrutinized using pre-specified and preprogrammed logic rules to detect outlier values and inconsistent data items. These will be flagged and checked for validity to ensure that reporting or data entry errors have not occurred.

64

This will be repeated one last time at the completion of the study, but before database lock. In addition to a daily tape backup, databases will be backed-up weekly onto DVDs that are stored in a secure off-site location with restricted access.

14.3 Electronic Facilitation of Follow-Up

The DCC will automatically generate a complete 24-month follow-up schedule for each subject that will be accessible to the Clinical Center within 2 business days of randomization. There will be continuous monitoring of visit completion and the Clinical Centers will be contacted if reporting has not occurred within 7 days of a scheduled visit. If this does not elicit a response or a completed report within 7 days, an electronic reminder will be sent to the Center. If there is no completed report within a further 7 days, the Clinical Center research coordinator, Clinical Center investigator, and ATTRACT Clinical Coordinating Center will be informed of the reporting deficit. This process is expected to achieve timely reporting of nearly all scheduled visits.

14.4 Data Confidentiality

14.4.1 At the Data Coordinating Center

- Personal identifiers (e.g., name, address, telephone numbers) will not be entered in the electronic database (this data will be stored in a secure location in the Clinical Centers with restricted access) and will be removed from all patient material sent to the DCC for clinical outcomes adjudication (e.g., clinic notes, x-rays). Centers that are unable to deidentify imaging exams may submit the exams provided that doing so is consistent with the signed informed consent form and HIPAA Authorization approved by the local IRB.
- 2. Clinical Centers will require a complex password to gain access to Web-based documents.
- 3. The DCC database will be password protected with strong encryption and will incorporate various fire walls and isolated networks.
- 4. All attempts to access the DCC database will be logged.
- 5. All data will be destroyed after 25 years.
- All DCC practices will comply with McMaster University and Hamilton Health Sciences joint policy "Standard Operating Procedures for Clinical Research" and applicable OCOG SOPs related to DCC activities.

14.4.2 At the Clinical Centers, Clinical Coordinating Center, and Core Laboratories

Subject data will be kept in a locked office and on password-protected and firewall-protected computer systems, and will only be available to the research team. Different password-

protected files will be created and will be linked using the participant's unique identification number. Subject names and other personal information will be kept separate from study data. Identifier keys will be stored in separate files which only the site principal investigator and authorized personnel at the site, CCC, or core laboratory can access. A list of names of all personnel who are approved to have such access will be maintained at each Clinical Center.

14.5 Compliance with Laws and Regulations

This study will be conducted in accordance with current FDA Good Clinical Practices, the Health Insurance Portability and Accountability Act (HIPAA), and local ethical and legal requirements.

15 STATISTICAL METHODS

15.1 Sample Size Calculation

The goal of the ATTRACT Trial is to determine if adjunctive PCDT (Experimental Arm), compared with optimal standard DVT therapy alone (Control Arm), reduces the 2-year occurrence of PTS in subjects with symptomatic proximal DVT. Based on previous studies (2-5), 30% of subjects in the Control Arm are expected to have PTS within 24 months of DVT diagnosis. Based on the expected success of PCDT at restoring venous patency and reductions of PTS that were achieved with thrombolytic therapy in earlier studies (33,34,42,51,52,139), we hypothesize that PCDT will reduce the risk of PTS by at least 33%. Accepting a 5% chance of incorrectly concluding that there is a difference in the proportion of subjects with PTS at 24 months with PCDT (α error=0.05; two-sided), and the requirement that the study has an 80% chance (β error=0.2) of detecting a true difference if PCDT truly reduces PTS by 33%, 311 subjects in each group must be studied (based on the Fisher's exact test).

In recently completed studies of long-term treatment for unprovoked VTE coordinated by the DCC, loss to follow-up or death occurred in 2.5% during 2 years follow-up (140), and in 3.4% during mean follow-up of 2.4 years (141). We therefore expect no more than 5% of randomized subjects to be lost to follow-up at 24 months. However, to ensure that statistical power will not be compromised, we will assume that as many as 10% of randomized subjects (double the maximum expected) will not complete the 24-month assessment. Therefore, we plan to randomize 346 subjects to each group, yielding a total study sample size of **692 subjects**.

For the secondary analyses, 692 subjects will provide approximately 88% power to detect an effect size of 0.25 with continuous outcomes. QOL changes from baseline: This translates into the ability to detect a difference of 1.25 in the VEINES-QOL change scores, and 2.5 in the SF-36v2 PCS and MCS change scores (change of 4 points is clinically important for all 3 scales).

PTS severity on Villalta PTS Scale: A difference as small as 1.25 units can be detected (5-point gradations define severity categories) (98, 111). Ultrasound outcomes: Assuming a 50% risk of deep venous reflux in the Control Arm and 10% inflation for losses due to withdrawal, death, or inadequate exams (rare), 142 subjects will provide 80% power to detect a 50% relative risk reduction for this outcome (alpha = 0.05, two-sided). 128 evaluable subjects will provide 80% power to detect effect sizes of 0.5 for reflux and obstruction on the continuous VSDS scales.

Regarding safety, we will perform a descriptive analysis of the rates of major bleeding and symptomatic PE in the two study Arms. These events are expected to occur infrequently (2% for major bleeding at 10 days and for symptomatic PE at 3 months) in the Control Arm. With 311 evaluable subjects per arm, if 2% of each group experiences an outcome, the 95% confidence interval on the difference of 0% will include an absolute decrease or increase of 2.4%.

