15.3 Secondary Analyses

Secondary analyses will be performed using both analysis sets. To account for multiple testing, a two-sided p-value of 0.01 or less will be considered statistically significant for all tests (144).

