15.3.5 Generic Quality of Life

The change in SF-36v2 PCS and MCS scores from baseline to 24 months will be compared between the two groups using a Student's t-test. A difference of 5 points on each scale is considered to be clinically relevant. In addition, a linear mixed model analysis of the repeated assessments (at 1, 6, 12, 18 and 24 months) with baseline scores as a covariate will be used to investigate the changes over time, and if they differ by treatment arm.

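### Section 15.1 states secondary-outcome power of 88% and 80% at alpha 0.05, but Section 15.3 tests at 0.01, where power is about 70% and 58%

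*Protocol*

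**What the plan says.** Section 15.1 gives three power statements beyond the primary outcome.

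- Continuous secondary outcomes: "For the secondary analyses, 692 subjects will provide approximately 88% power to detect an effect size of 0.25 with continuous outcomes". No alpha stands beside this figure. It is translated into 1.25 points on VEINES-QOL, 2.5 on the SF-36v2 component scores and 1.25 on Villalta.
- Ultrasound reflux, with a 50% control risk: "142 subjects will provide 80% power to detect a 50% relative risk reduction for this outcome (alpha = 0.05, two-sided").
- Ultrasound VSDS scores: 128 evaluable subjects give 80% "power to detect effect sizes of 0.5 for reflux and obstruction on the continuous VSDS scales", again with no alpha stated.

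Section 15.3 then sets the threshold for the secondary analyses: "a two-sided p-value of 0.01 or less will be considered statistically significant for all tests". The quality-of-life scales (15.3.4, 15.3.5), Villalta severity (15.3.6) and the VSDS comparison (15.3.10) all sit under that heading. Nothing in the protocol exempts them or restates their power at 0.01.

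On what counts as important, Section 15.1 uses 4 points for VEINES-QOL and both SF-36 components. Section 15.3.5 says of the two SF-36 scales: "A difference of 5 points on each scale is considered to be clinically relevant".

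**The concern.** Stated power tells a reader how much weight a null result can bear. If it was computed at a looser threshold than the one used for testing, a null secondary result appears more informative than it is. At an effect size of 0.25 the chance of missing a true effect would be about 30% rather than 12%. For the VSDS scores at 0.5 it would be about 42% rather than 20%. The ultrasound comparison matters most, because Section 8.13 sets up that substudy to ask whether preventing reflux or obstruction explains any effect on post-thrombotic syndrome.

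**Working it through.** **Inputs**
- Main trial: "311 subjects in each group must be studied (based on the Fisher's exact test"), and "we plan to randomize 346 subjects to each group" after allowing 10% loss. So 311 per arm are evaluable, or 346 with no losses (15.1).
- Ultrasound: 142/2 = 71 per arm enrolled, 128/2 = 64 evaluable; effect size 0.5 for VSDS, and 50% versus 25% for reflux (15.1).
- Alpha: 0.05 as stated for reflux; 0.01 from 15.3.
- Implied SDs: 1.25/0.25 = 5 (VEINES-QOL, Villalta) and 2.5/0.25 = 10 (SF-36).

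**Method for means.** Two-sided t-test, noncentrality d·√(n/2), 2n − 2 degrees of freedom. The normal approximation is Φ(d·√(n/2) − z), with z = 1.960 at 0.05 and 2.576 at 0.01.

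**Step 1: reproduce the plan's figures at 0.05**
- 311 per arm, d = 0.25: 0.25 × √155.5 = 3.117; Φ(3.117 − 1.960) = 87.7% (t-test 87.5%). This matches 88%. With 346 per arm the result is 91%, so the plan's figure rests on the evaluable number although it is attributed to 692 subjects.
- VSDS, 64 per arm, d = 0.5: 0.5 × √32 = 2.828; Φ(2.828 − 1.960) = 81% (t-test 80%). Matches.
- Reflux, 64 per arm, Fisher's exact test by full enumeration: 80.2%. Matches. The uncorrected chi-square (normal approximation) gives 84%, so Fisher appears to be the basis.

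**Step 2: the same designs at 0.01**

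| Outcome | n per arm | Stated | At 0.01 |
|---|---|---|---|
| Continuous, d = 0.25 | 311 | 88% | Φ(3.117 − 2.576) = 70.6%; t-test 70.3% |
| Continuous, d = 0.25 | 346 | – | Φ(3.288 − 2.576) = 76.2%; t-test 75.9% |
| VSDS, d = 0.5 | 64 | 80% | Φ(2.828 − 2.576) = 60.0%; t-test 58.5% |
| VSDS, d = 0.5 | 71 | – | t-test 64% |
| Reflux, 50% vs 25% | 64 | 80% | Fisher 57.9%; uncorrected chi-square 64.0% (normal approximation), 64.7% (enumerated) |

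No row reaches 88% or 80% at 0.01, even with every randomized subject. That makes 0.05 a firm inference for the two figures printed without an alpha.

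**Step 3: what the design can detect at 0.01**
- 88% power, 311 per arm: d = (2.576 + 1.175)/√155.5 = 0.30. In points: 0.30 × 5 = 1.5 on VEINES-QOL, 0.30 × 10 = 3.0 on SF-36, and 0.30 × 5 = 1.5 on Villalta.
- 80% power for VSDS, 64 per arm: d = (2.576 + 0.842)/√32 = 0.60 (t-test 0.61).

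**Step 4: power at 0.01 for the differences the protocol calls important (311 per arm)**
- SF-36, 4 points: d = 4/10 = 0.4; 0.4 × √155.5 = 4.988; Φ(4.988 − 2.576) = 99.2%.
- SF-36, 5 points: d = 0.5; power above 99.9%.
- VEINES-QOL, 4 points: d = 4/5 = 0.8; power above 99.9%.

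**The case against.** The strongest reply is that little turns on this for the main trial. Section 15.1 uses the 0.25 effect size mainly to show that the detectable differences are well below 4 points, and Step 4 shows that remains true at 0.01. A reader might infer from the drop to 70% that the quality-of-life comparisons are underpowered. The protocol's own figures do not support that: a null result would still argue strongly against a 4-point difference. This part of the objection stands and limits the severity.

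On the ultrasound side, three points stand in part.
- The reflux figure is openly labelled alpha 0.05, so its basis is not hidden. It still conflicts with Section 15.3 if reflux is tested there.
- Section 15.3.10 names a t-test for the VSDS scores but no between-arm test of binary reflux. Prevalence of reflux is a secondary outcome in Section 8.2, so applying 0.01 to it is reasonable but inferred. Because no test is named, its power is best given as a range, 58% to 65%.
- A reader might conclude that the substudy's mechanism question has little better than even odds of an answer. That goes too far. The figures concern only the between-arm comparison at one chosen effect size. Section 15.3.10 also correlates the scores with post-thrombotic syndrome, and these calculations do not address that.

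The arithmetic in Section 15.1 is correct at 0.05. The fault is the disagreement over alpha between the two sections.

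**Conclusion.** The inconsistency is real and should be corrected. At the protocol's own threshold, power for an effect size of 0.25 is about 70%, not 88%. Power for the VSDS scores at 0.5 is about 58%, not 80%, and for reflux it is about 58% (Fisher) to 65% (uncorrected chi-square). The more favourable 76% (continuous outcomes) and 64% (VSDS) apply only with no losses.

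The consequence is modest for quality of life and Villalta severity, where the detectable differences rise only from 1.25, 2.5 and 1.25 points to about 1.5, 3.0 and 1.5. The quality-of-life values stay below the stated clinically important differences, and 1.5 Villalta points is small against that scale's 5-point severity gradations. The consequence is larger for the ultrasound between-arm comparison, where the protocol gives no clinically important VSDS difference to fall back on. The primary analysis, tested at 0.05 under Section 15.2, and the sample size are unaffected.

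These results assume equal arms, the evaluable numbers in Section 15.1, the SDs implied by its point differences, and alpha 0.05 behind the two figures that state none. The 4- versus 5-point SF-36 mismatch is a separate, minor matter: neither value enters a test.

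**What to change.** Restate the secondary power in Section 15.1 at two-sided alpha 0.01, with the alpha and evaluable numbers printed beside each figure:
- Continuous outcomes, 311 evaluable per arm: about 70% power at effect size 0.25, or 88% at about 0.30 (about 1.5 VEINES-QOL, 3.0 SF-36 and 1.5 Villalta points).
- Ultrasound, 64 evaluable per arm: about 58% power for VSDS at 0.5, or 80% at about 0.61; about 58% for reflux of 50% versus 25% if Fisher's exact test is intended, with the test named.

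Keep the 0.01 rule. Exempting the substudy from it would loosen multiplicity control merely to preserve a power figure. As a separate edit, use one clinically important SF-36 difference in Sections 15.1 and 15.3.5.

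The cost is wording and recalculated figures only. No subjects, visits or analyses are added. The change should be made before unblinding.
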